**Table 1: Planned Study Enrollment**

Total Number	Genotype	Enrollment Targets	Fibrosis Stage
N = 280	1a	n = 75	F0-F4 (Target: 20% with compensated cirrhosis)
	1b	n = 40	
	2	n = 40	
	3	n = 75	
	4	n = 25	
	5, 6, or 7	n = 25	F0-F4 (No specified target for compensated cirrhosis)

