### 4.2. Inclusion Criteria

1. Willing and able to provide written informed consent
2. Male or female subjects between  $\geq 18$  years of age (or the legal age of consent per local regulations) and  $\leq 85$  years of age
3. Fridericia-corrected QT (QTcF) interval  $\leq 440$  ms for males and  $\leq 460$  ms for females at Screening  
*Note: The mean of the triplicate readings, rounded to the nearest whole number, should be used to assess the QTcF.*
4. Female subjects of childbearing potential: agreement to remain abstinent (refrain from heterosexual intercourse) or to the use of an acceptable effective contraception, as described in Section 5.9
5. Females of childbearing potential must have a negative pregnancy test at Screening and at Day 1 prior to dosing
6. Subjects must be DAA-treatment-naïve, defined as never exposed to an approved or experimental DAA for HCV  
*Note: Prior exposure to (peg)interferon with or without ribavirin is acceptable, as long as it/they were not administered with a DAA.*
7. Willingness to provide a blood sample at Screening for genotyping.
8. Documented medical history compatible with chronic HCV, including any one of the following:
  - a. positive for anti-HCV antibody, HCV RNA, or an HCV GT at least 6 months prior to Day 1, or
  - b. positive for anti-HCV antibody at Screening with clinical or laboratory evidence of chronic HCV disease, such as the presence of fibrosis by biopsy or noninvasive tests

9. HCV RNA  $\geq$  1,000 IU/mL at Screening.
10. Liver disease staging assessment as follows:
  - Absence of cirrhosis (F0 to F3) defined as any one of the following:
    - Liver biopsy within 24 months of Day 1 showing absence of cirrhosis
    - Fibroscan® within 12 months of Day 1 with a result of  $\leq$  12.5 kPa
    - Fibrosure® (Fibrotest®) performed during screening with a score of  $\leq$  0.48 and an aspartate aminotransferase (AST)-to-platelet ratio index (APRI) of  $\leq$  1
  - Compensated cirrhosis (F4) defined as any one of the following:
    - Liver biopsy performed prior to Day 1 showing cirrhosis (Metavir stage 4 or equivalent)
    - Fibroscan® within 12 months of Day 1 showing cirrhosis with result  $>$  12.5 kPa
    - Fibrosure® (Fibrotest®) performed during screening with a score of  $>$  0.75 and an APRI of  $>$  2

*NOTE: Subjects in the lead-in group must not have F4 cirrhosis*

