### **5.6.2. Individual Safety Stopping Rules**

Treatment will be discontinued in any subject who experiences any one of the following:

- Confirmed elevation of ALT and/or AST  $> 5 \times$  baseline or post-baseline nadir, and  $> 5 \times$  ULN
- Confirmed elevation of ALT and/or AST  $> 15 \times$  ULN
- Confirmed elevation of ALT and/or AST  $> 3 \times$  post-baseline nadir, is  $> 3 \times$  ULN, and total bilirubin  $> 2 \times$  ULN, without any alternative causes or reason for these elevations
- Confirmed new onset  $\geq$  grade 3 elevation in creatinine or decreased GFR  $< 30 \text{ mL/min}/1.73 \text{ m}^2$
- Any SAE or grade 4 AE (including any confirmed grade 4 laboratory abnormality reported as an AE) that are considered by the investigator to be related to study drugs, *Note: To warrant treatment discontinuation, a grade 4 laboratory abnormality should have clinical findings expected to be associated with the laboratory abnormality. Subjects with isolated asymptomatic laboratory abnormalities without any clinical correlations are allowed to remain on treatment with continued monitoring according to the preference of the investigator.*
- Pregnancy during treatment (i.e., in female study subjects)

A confirmed value is defined as one that is repeated at the next subsequent test. Any of the above laboratory results and all  $\geq$  grade 3 new onset laboratory abnormalities must be repeated as soon as possible, preferably within 48 hours upon reporting of the initial value.

Additional follow-up and medical care, beyond what is specified in the protocol, is described in Section 5.6.3.

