### **5.6.3. Study Stopping Rules**

The study will be paused in any of the following scenarios:

- If > 3 of the first 60 subjects experience (a) confirmed elevation of ALT and/or AST > 5 x baseline or post-baseline nadir, and > 5 x ULN OR (b) confirmed elevation of ALT and/or AST > 15 x ULN OR (c) any SAE or grade 4 AE which are considered by the investigator to be related to study drugs
- If > 15 subjects at any time during the trial experience (a) confirmed elevation of ALT and/or AST > 5 x baseline or post-baseline nadir, and > 5 x ULN OR (b) confirmed elevation of ALT and/or AST > 15 x ULN
- Any SAE or grade 4 AE which is considered by the investigator to be related to study drugs
- After three or more similar grade 3 or higher AEs considered by the investigator to be related to study drugs

Any of these circumstances will result in no additional subjects being enrolled. Subjects who are tolerating treatment may continue to receive study drugs. The Sponsor will collect and review all the available data with the clinical investigators and with regulatory authorities, to obtain agreement on a plan forward.

*Note: ALT/AST increases associated with virologic failure would not trigger the above stopping rules.*

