- Is an important medical event that may jeopardize the subject or may require intervention to prevent one of the other outcomes listed above (according to medical judgment of the qualified investigator)

Laboratory abnormalities without clinical significance are not recorded as AEs or SAEs. However, laboratory abnormalities that require medical or surgical intervention or lead to study drug interruption, modification, or discontinuation must be recorded as an AE, as well as an SAE, if they meet the definition above. In addition, laboratory or other abnormal assessments (eg, ECG, X-rays, vital signs) that are associated with signs and/or symptoms must be recorded as an AE or SAE if they meet the definition of an AE or SAE as described above. If the laboratory abnormality is part of a syndrome, record the syndrome or diagnosis (e.g., anemia), not the laboratory result (i.e., decreased hemoglobin). Laboratory abnormalities that do not require medical intervention or action are generally not considered AEs.

Laboratory abnormalities will be graded based on the Division of AIDS (DAIDS) Table for Grading the Severity of Adult and Pediatric Adverse Events, Version 2.1 . If a value falls within the local laboratory normal range, then it will not be graded. For AEs associated with laboratory abnormalities, the event should be graded on the basis of the clinical severity in the context of the underlying conditions; this may or may not be in agreement with the grading of the laboratory abnormality.

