## **8. STATISTICAL ANALYSES**

The following sections briefly summarize the statistical analysis. A statistical analysis plan (SAP) describing the detailed methodology will be prepared prior to database lock.

Results of all efficacy analyses will be presented by genotype and cirrhotic status.

Interim and final analyses will be reported/posted in accordance with local/regional requirements.

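### Safety tables are not split by cirrhotic status, although every planned cirrhotic subject enrols after the non-cirrhotic lead-in

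*Protocol*

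**What the plan says.** **Who enrols when.** Protocol 4.2 states: "Subjects in the lead-in group must not have F4 cirrhosis". Table 1 sets the cirrhosis target for GT1-4 as "F0-F4 (Target: 20% with compensated cirrhosis" and sets none for GT5-7. Every planned cirrhotic subject is therefore among the 220 enrolled after the lead-in.

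**Study-level pause rules (Protocol 5.6.3).** The first rule covers only the first 60 subjects. The second is a trial-wide pooled count: "If > 15 subjects at any time during the trial experience (a) confirmed elevation of ALT and/or AST > 5 x baseline", with further conditions on multiples of the upper limit of normal. The other two depend on the investigator judging the event related: "Any SAE or grade 4 AE which is considered by the investigator to be related to study drugs" and "After three or more similar grade 3 or higher AEs considered by the investigator to be related to study drugs". None mentions cirrhosis.

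**Individual protection.** Protocol 5.6.2 opens with "Treatment will be discontinued in any subject who experiences any one of the following" and lists the same ALT/AST criteria plus a combined ALT/AST and bilirubin criterion. Protocol 7.1 adds that "laboratory abnormalities that require medical or surgical intervention or lead to study drug interruption, modification, or discontinuation must be recorded as an AE".

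**Reporting.** Protocol Section 8 says: "Results of all efficacy analyses will be presented by genotype and cirrhotic status". SAP 8.5 lists cirrhotic status as a subgroup, within the Efficacy chapter. Protocol 8.5 and SAP 9.1, 9.2 and 9.5 describe AE and laboratory summaries with no such split. SAP 9.1 uses the safety population as a whole.

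**The concern.** Safety and tolerability is a primary objective (Protocol 2.1), and the regimen is meant for patients with or without cirrhosis (Protocol 1.3). Cirrhotics are the subgroup in which a liver effect would matter most and the one about which the lead-in safety evaluation can say nothing. They will make up about a fifth of the trial. In pooled AE and shift tables, a liver event rate several times higher in cirrhotics can look like a low overall rate. A reader of the study report would then see efficacy by cirrhotic status but could not judge from the tables whether the liver safety profile also holds in that group.

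The pooled pause count has the same property on a smaller scale. The remaining study-level rules depend on attribution to study drug, which may be less likely when a liver event can be put down to the underlying cirrhosis.

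**Working it through.** The plan gives no derivation or operating characteristics for its count of more than 15, so there is no stated figure to reproduce. All event rates, attribution shares, enrolment rates and lags below are assumptions.

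**1. Number of cirrhotics (Protocol Table 1).** GT1-4 targets: 75 + 40 + 40 + 75 + 25 = 255, and 0.20 x 255 = 51. If the target is read as applying to all 280: 0.20 x 280 = 56. With 51, there are 280 - 51 = 229 others.

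**2. Dilution in the planned tables.** Assume 15% in cirrhotics and 1% in the others.
- Expected events: 0.15 x 51 + 0.01 x 229 = 7.65 + 2.29 = 9.94.
- Pooled rate: 9.94/280 = 3.55%, about 3.6%.
- With 56 cirrhotics: (8.40 + 2.24)/280 = 3.8%.

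**3. What a split would show.** Take whole numbers near those expectations: 8/51 = 15.7% and 2/229 = 0.9%, pooled 10/280 = 3.6%. The Wilson 95% interval for 8/51, with z = 1.96, has centre (0.1569 + 3.84/102)/(1 + 3.84/51) = 0.181 and half-width 0.099, so 8.2% to 28.0%. For 2/229 the same formula gives 0.2% to 3.1%. The intervals are wide, but the contrast is visible. The pooled table hides it.

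**4. The pooled pause count.** With 1% in the 229 others, 16 events are expected only when the cirrhotic rate is (16 - 2.29)/51 = 26.9%. The chance that the total exceeds 15 (sum of two independent binomials) is:

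| Cirrhotic rate | 51 cirrhotics | 56 cirrhotics |
|---|---|---|
| 10% | 0.3% | 0.5% |
| 15% | 3.7% | 6.2% |
| 20% | 17% | 26% |
| 30% | 71% | 83% |

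**5. An optional review prompt at more than 3 cirrhotics.** P(Bin(51, p) > 3):

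| True cirrhotic rate | Prompt reached |
|---|---|
| 1% | 0.2% |
| 2% | 1.9% |
| 3% | 6.7% |
| 4% | 14.6% |
| 5% | 25% |
| 10% | 76% |
| 15% | 96% |

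**6. How much the causality-based rules already do.** A simulation kept the trial-wide count and both causality-based rules active. It assumed 15% in cirrhotics, 1% in others, 10 subjects per week and confirmation 1 to 9 weeks after enrolment.

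| Events judged related and grade 3+ | Of all events, related SAE or grade 4 | Existing rules ever pause | Prompt is the only formal flag |
|---|---|---|---|
| 10% | 2.5% | 26% | 71% |
| 20% | 5% | 49% | 47% |
| 50% | 10% | 90% | 8% |

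At a 5% cirrhotic rate with the middle row's shares, the prompt is the only formal flag in 17%.

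**The case against.** **Subjects are already protected.** A reader might infer that the pooled count leaves cirrhotics unguarded, or that liver harm in them would go undetected. The documents do not support that. Each affected subject stops treatment (Protocol 5.6.2), and the event is recorded as an AE and assessed for causality (Protocol 7.1, 7.1.2). SAEs reach the sponsor within 24 hours whatever the causality (Protocol 7.3), and the trial is open-label with central laboratory testing. One related SAE or grade 4 AE, or three similar related grade 3 AEs, pauses enrolment. This objection stands and limits the point to a backstop and reporting gap. One qualification: Protocol 7.1 grades a laboratory-based AE on clinical severity, so an asymptomatic confirmed ALT rise can stop treatment yet be graded below 3 and not count towards the three-event rule.

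**The assumed rates have no support in the documents.** This also stands. Protocol 1.1 and 1.2.2 report no worrying laboratory pattern with BEM, including 7 days in Child-Pugh A subjects, or with RZR plus uprifosbuvir for 12 weeks in studies that included cirrhotics. Neither is the BEM + RZR combination.

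**The split could be added at report stage.** All AEs are listed (SAP 9.1) and cirrhotic status is summarised at baseline (SAP 7.4), so this is true. A split chosen after the data are seen carries less weight than a planned one, and planning it costs almost nothing. SAP 8.5 does not confine itself to efficacy in so many words, but it sits in that chapter and Section 9 does not refer to it.

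**A prompt at more than 3 is itself a flat count.** Four events are 40% of the first 10 cirrhotics and 7.8% of 51. This stands and is one reason to keep the prompt optional.

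**Stepped pause counts.** A reader might want intermediate pooled limits, such as more than 6 of the first 120, 9 of 180 and 12 of 240. In the 20% row of step 6 they raise pauses by the end of enrolment only from 37% to 41%, and in the 50% row not at all. At a flat true rate of 4%, pauses from the count rules rise from 27% to 37%. The gain does not justify the change.

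**Conclusion.** The point holds for reporting. Safety is a primary objective and every planned cirrhotic enrols after the lead-in, yet no planned safety table separates them, while efficacy is separated. The size depends on assumed rates: 15% against 1% would appear as about 3.6% pooled. That the dilution occurs follows from the planned numbers alone and needs no assumption about attribution.

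For the pause rules the point is weaker. The pooled count is insensitive to a signal confined to cirrhotics, but it is not the only safeguard. A cirrhotic-specific review would add something mainly if about 20% or fewer of such events are judged related and grade 3 or higher. If about half are, it adds little. The documents do not support reading this as a failure of detection or as a reason to rewrite the pause rules.

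**What to change.** **Main change.** In SAP 9.1-9.2, add cirrhotic status (non-cirrhotic, compensated cirrhosis) to the treatment-emergent AE summaries. In SAP 9.5, add it to the toxicity-grade and shift tables for ALT, AST and bilirubin. The variable already exists for the efficacy subgroups. The cost is a few more tables, and estimates from about 51 subjects will be imprecise, so they should be read descriptively. The change can be made at any time before database lock and pauses nothing.

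**Optional and secondary.** Have the sponsor's medical monitor review the data when more than three cirrhotic subjects meet the ALT/AST criteria of Protocol 5.6.3, as a review and not a pause. A safety monitoring plan is the better place. Written into Section 5.6.3, it would be a protocol amendment needing IRB/IEC submission (Protocol 11.1). The cost is some reviews at modest true rates, as step 5 shows: 6.7% of trials at 3%, 14.6% at 4% and 25% at 5%.

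Leave the existing pause counts as they are.

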## 5.7. Premature Discontinuation

Subjects may voluntarily discontinue treatment or withdraw from the study at any time. They may also be removed from the study at the discretion of the investigator or Sponsor at any time. The investigator may withdraw a subject at any time if it is determined that continuing the study would result in a significant safety risk to the subject.

Premature treatment discontinuation may occur for any of the following reasons:

- Noncompliance with the protocol requirements
- Pregnancy
- On-treatment virologic failure, as defined in Section 5.6.1
- Adverse event precluding further study participation due to safety concerns or compliance issues
- Subject request
- Investigator request
- Sponsor request

Subjects who prematurely discontinue treatment should have an Early Termination (ET) visit and be asked to return for the scheduled post-treatment follow-up visits.

In subjects who require additional care after their participation in the trial has ended or been completed, such as that necessary to monitor an AE(s), continued follow-up and care will be

provided until resolution of the AE(s). For those who experience a lack of efficacy and virologic failure, refer to Section [5.6.1](#) for additional reimbursable treatment/care.

## **5.8. Prior Therapy, Concomitant Therapy, Permitted Therapy, Cautionary Therapy, and Prohibited Therapy**

### **5.8.1. Prior Medication**

- Subjects must be DAA-treatment-naïve, except that prior exposure to (peg)interferon with or without ribavirin is acceptable as long as it was not administered with a DAA (inclusion criterion 7, Section [4.2](#)).
- Subjects are prohibited from use of other investigational drugs within 30 days prior to dosing in this study (exclusion criterion 6, Section [4.3](#))

### **5.8.2. Concomitant Medication**

Concomitant therapy consists of any medication (eg, prescription drugs, over the counter drugs, vaccines, herbal or homeopathic remedies, nutritional supplements) used by a subject in addition to study drug treatment. All such medications should be reported to the investigator and recorded on the Concomitant Medications electronic Case Report Form (eCRF). Concomitant medications should be used according to their label.

### **5.8.3. Permitted Therapy**

Subjects are also permitted to use the following therapies during the study:

- Acetaminophen (paracetamol), ibuprofen
- Anti-inflammatory drugs
- Prophylactic anticoagulation with low-dose aspirin, direct factor Xa inhibitors, or direct thrombin inhibitors
- Prescribed medications for concomitant conditions as per medical history, such as chronic supplementary oxygen, antihypertensives, antidiabetic medications, rheumatologic medications, or respiratory medications (e.g., chronic inhaled/intranasal/oral steroids)
- Hormonal contraceptives (see Section [5.9](#))
- Hormone replacement therapy
- Direct acting COVID medications (Paxlovid, molnupiravir, remdesivir, favipiravir, monoclonal antibodies, convalescent plasma). See Section [5.8.5](#) for additional details.
- Other COVID standard-of-care (SOC) therapies without direct antiviral effects (i.e., corticosteroids)

### **5.8.4. Cautionary Therapy**

#### **Herbal Therapies**

Concomitant use of herbal therapies is not recommended because their PK, safety profiles, and potential drug-drug interactions (DDIs) are generally unknown.

### **Mitigation of Other Potential DDIs**

COVID treatments with concerns for DDIs:

While remdesivir and Paxlovid are permitted, staggered dosing as specified below must be followed to minimize DDI.

Remdesivir:

As BEM and remdesivir share a common target and metabolic activation pathway, there is a potential for PK or PD drug interactions between the two, during concomitant administration of both drugs. Study drug must be dosed at least 2 hours before remdesivir.

Paxlovid:

As ritonavir is a major P-glycoprotein (P-gp) inhibitor (see below), subjects enrolled in the study who are taking Paxlovid should not take Paxlovid until at least 2 hours after taking BEM/RZR. See below for additional P-glycoprotein – based DDIs

For more details regarding potential DDIs, refer to the BEM and RZR Investigator's Brochures.

### **P-glycoprotein-Based Inhibition**

Concomitant use of P-gp inhibitors is permitted but must be taken at least 2 hours after administration of study drug. Common examples of P-gp inhibitors include cyclosporine, carvedilol, imidazoles, macrolides, ritonavir, and verapamil.

For a full list of P-gp inhibitors, refer to: <https://go.drugbank.com/categories/DBCAT002667>

Subjects taking digoxin must do so at least 2 hours after taking study drug.

### **Gastrointestinal Acid Reduction-Based Interaction**

Gastrointestinal acid reducing agents such as proton-pump inhibitors, H2 blockers and antacids may reduce the solubility of BEM. Subjects taking these agents will do so at least 2 hours after taking study drug.

Permitted concomitant medications should be administered only as medically necessary during the study. Any use of concomitant medications should be recorded and entered into the case report form.

For more details regarding the effects of co-administered therapies on RZR and BEM, refer to the respective Investigator's Brochures.

### **5.8.5. Prohibited Therapy**

Concomitant use of the following is prohibited:

- Investigational drugs (other than protocol-mandated study treatment)
- HCV treatments (other than protocol-mandated study treatment)
- Hydroxychloroquine or amiodarone

- Strong and moderate inducers of cytochrome P450 3A and/or P-gp including anti-infectives (nafcillin, rifampin), anticonvulsants (carbamazepine, phenytoin, phenobarbital), endothelin antagonists (bosentan), and wakefulness-promoting agents (modafinil). For a comprehensive list of cytochrome P450 3A inducers, refer to: <https://go.drugbank.com/categories/DBCAT000492>; for a comprehensive list of P-gp inducers, refer to: <https://go.drugbank.com/categories/DBCAT002666>

## 5.9. Contraception Requirements

A female is considered to be of childbearing potential if she is postmenarchal, has not reached a postmenopausal state ( $\geq 12$  continuous months of amenorrhea with no identified cause other than menopause), and is not permanently infertile due to surgery (i.e., removal of ovaries, fallopian tubes, and/or uterus) or another cause as determined by the investigator (e.g., Müllerian agenesis). The definition of childbearing potential may be adapted for alignment with local guidelines or regulations. Females of childbearing potential must be established on their chosen method of contraception at screening.

Female subjects of childbearing potential must agree to remain abstinent (refrain from heterosexual intercourse) or use one of the following methods of acceptable effective contraception during the treatment period and for 30 days after the final dose of study drugs:

- Bilateral tubal ligation
- Male sterilization
- Hormonal contraceptives
- Intrauterine devices (whether or not they are hormone-releasing)
- Male or female condom with or without spermicide (male and female condom cannot be used together)
- Sexual abstinence

*Note: The reliability of sexual abstinence should be evaluated in relation to the duration of the clinical trial and the preferred and usual lifestyle of the subject. Periodic abstinence (e.g., calendar, ovulation, symptothermal, or post-ovulation methods) and withdrawal are not adequate methods of contraception. If required per local guidelines or regulations, locally recognized adequate methods of contraception and information about the reliability of abstinence will be described in the local Informed Consent Form (ICF).*

- Cap, diaphragm, or sponge with spermicide.

Should acceptable effective methods of contraception be more restrictive than the methods listed above per local regulations, guidance, or investigator practice, a more restrictive list may be included within the site/country-specific Institutional Review Board (IRB)/Independent Ethics Committee (IEC)-approved ICF.

